1.4 Study Conduct

This study will be conducted in compliance with the current protocol approved by the Institutional Review Board and according to Good Clinical Practice standards. All study documents will be posted on a secure document management site. No deviation from the protocol will be knowingly implemented without the prior review and approval of the IRB except where it may be necessary to eliminate an immediate hazard to a research subject. In such case, the deviation will be reported to the IRB as soon as possible.

2 Study Objective

Our goal in this project is to demonstrate the feasibility of a novel intervention, targeted gown and glove use, to decrease SA acquisition and SA infection as a precursor for a future multisite stepped wedge cluster trial. Our targeted intervention limits both cost and stigma while blocking the transmission and acquisition of multiple organisms.

Objective 1: To implement a targeted gown and glove intervention in two community-based nursing homes.

Expected Outcome 1: A targeted gown and glove intervention can be successfully implemented across two community-based nursing homes with >80% compliance with gown and glove use for high risk care in high risk residents.

Objective 2: To evaluate the impact of a targeted gown and glove intervention on SA acquisition and SA infection rates.

Expected Outcome 2a: The intervention will decrease SA acquisition and infection rates.

Expected Outcome 2b: We will determine the effect size to guide the design (including the sample size) of a future trial.

Objective 3: To develop an implementation “toolkit” that can be easily adapted and implemented at nursing homes in a future trial.

Expected Outcome 3: Barriers to and strategies for implementation of the targeted gown and glove intervention will be identified leading to modification of the pilot intervention and development of an implementation “toolkit” for a future trial.

3 Study Design

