3.1 Primary Study Endpoints/Secondary Endpoints

Outcome 1: Compliance with each component of the intervention (identification and flagging of high risk residents, use of gowns and gloves for high risk care) based on 1) weekly point prevalence studies for high risk residents and 2) weekly observations of high risk care interactions with 5-10 residents over the 2-month intervention periods. There will also be weekly observations of high risk care interaction of 5-10 residents over the 2-month baseline period to assess the change in gown and glove use.

Outcome 2a: The primary outcome will be a change in SA acquisition rates comparing baseline and intervention periods. Residents in the nursing home will be swabbed at the start of the study period, or when they are admitted. Then they will all be re-swabbed at discharge or when the study ends. Acquisition will be defined as a positive culture for a new SA in a resident who was negative for that SA at the start of the study period or admission. Cultures will be performed in the research lab using well established methods. Specimens will be saved for future evaluation of other bacteria. The secondary outcome will be invasive SA infections and other infections within 90 days of nursing home admission in residents as detected through surveillance from health care records including but not limited to CRISP, a state-wide central repository of health care records including hospital and nursing home discharge summaries.

Outcome 2b: The observed SA acquisition rate reduction from this pilot study will be used to estimate the effect size that will inform the sample size for a larger trial.

Outcome 3: We will qualitatively examine the acceptability of, and any barriers to implementation using broad stakeholder feedback. Elements found to be infeasible or unacceptable will be modified at each stage and an implementation toolkit will be developed for the future trial.

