Serious Adverse Events that are more likely than not (probably or definitely) related to the research will be reported immediately of the site investigator becoming aware of the SAE to the local IRB according to established IRB policy. The principal investigator will evaluate the adverse event and determine whether the adverse event affects the Risk/Benefit ratio of the study and whether modification to the protocol is required.

The principal investigator will conduct a review of all serious adverse events annually. The principal investigator will evaluate the frequency and severity of the serious adverse events and determine if modifications to the protocol is required. A summary of the serious adverse events will be reported to the UMB IRB annually, when renewal is sought.

10 **Statistical Plan**

10.1 **Data Analysis, Sample Size, and Precision**

For objective 1, we will calculate point estimates and 95% confidence intervals for the rates of compliance with each component of the intervention (identification and flagging of high risk residents, use of gowns and gloves for high risk care) as well as the change in gown and glove use for high risk care during the baseline and intervention periods. We will observe 40-80 encounters per nursing home where gowns and glove should be used which will result an estimate of the rate of compliance that is accurate +/- 8-10 percentage points.

For objective 2, we will estimate and compare the rates of transmission in the baseline and intervention periods in each nursing home. To estimate the rates from binary data, we note that the risk that a person acquires the infection in the interval between swabs can be written as $1-\exp(-\lambda t)$ where “ t ” is the number of days between swabs and λ is interpretable as the daily rate of acquisition. We will estimate λ in the baseline and intervention periods using maximum likelihood estimation and compare the two rates. Likelihood methods will be used to calculate a confidence interval for the ratio of the rates. This will be done for each nursing home separately. We will test 100 residents per nursing home per period which will result in an estimate of the rate of acquisition that is accurate +/- 4-6 percentage points. These estimates will give us insight into the effect size of the intervention and the variation between nursing homes for future planning.

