Proportion of Beds- Rehab or Skilled nursing	Facility Start-up	Administrator	Descriptive	Ratio
Proportion of Beds- Short stay	Facility Start-up	Administrator	Descriptive	Ratio
Resident to staff ratio by Type of HCW and Shift	Facility Start-up	Administrator	Descriptive	Ratio
Staff Infection Control Training	Facility Start-up	Administrator	Descriptive	Yes/no; record policy
Full time employees for Infection Prevention in Facility	Facility Start-up	Administrator	Descriptive	Interval
OUTCOME VARIABLES				
SA or other Infection	Within 90 days of at admission or study period start	MR	Outcome variable	Yes/no
SA colonization of Anterior nares	At admission or study period start/discharge or study period end	Culture	Outcome variable	Yes/no
SA colonization of Inguinal skin	At admission or study period start/discharge or study period end	Culture	Outcome variable	Yes/no
STAFF/HCW OBSERVATIONS (weekly for 5-10 high risk care activities in each nursing home during both the baseline period and the intervention period)				
Gown use	Observation visits	Observation	Study variable	Yes/no
Glove use	Observation visits	Observation	Study variable	Yes/no

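### At the 80% compliance target, 40–80 encounters per nursing home give about ±12.4 to ±8.8 points, not the stated ±8–10

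*Combined protocol and SAP*

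**What the plan says.** For Objective 1, Section 10.1 (Data Analysis, Sample Size, and Precision) commits to 95% intervals: "we will calculate point estimates and 95% confidence intervals for the rates of compliance with each component of the intervention". It then sets the number of observations, "We will observe 40-80 encounters per nursing home where gowns and glove should be used", and continues directly with the precision claim, "which will result an estimate of the rate of compliance that is accurate +/- 8-10 percentage points".

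The section gives no assumed compliance rate, no interval method and no allowance for repeat observations of the same residents or staff. The only compliance rate in the documents is Expected Outcome 1 in Section 2, which looks for implementation "across two community-based nursing homes with >80% compliance with gown and glove use for high risk care in high risk residents".

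The count of 40–80 matches the observation schedule. The Appendix table describes staff observations as "weekly for 5-10 high risk care activities in each nursing home during both the baseline period and the intervention period", and Section 3.1 describes "weekly observations of high risk care interactions with 5-10 residents over the 2-month intervention periods".

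**The concern.** A half-width for a proportion depends on the rate, the sample size and the confidence level. The plan fixes the last two and leaves the rate out. When the plan's own target is used as the rate, the low end of the planned range misses the stated precision.

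This sentence is the only justification given for the number of observations behind Objective 1, whose success is expressed as compliance above 80%. A reader who relies on ±10 would take an observed 80% in one home to exclude true compliance below about 70%. With 40 encounters it does not. The pilot is also meant to prepare a larger trial, so the figure may be reused when observation numbers are planned there.

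**Working it through.** **Inputs**

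- Confidence level: 95%, two-sided, z = 1.96 (Section 10.1).
- Encounters per home: 40 to 80 (Section 10.1). Check: 5 per week × about 8 weeks = 40, and 10 × 8 = 80 (Section 3.1 and Appendix).
- Compliance rate p: not stated for this calculation. I assume p = 0.80 from the target in Section 2 and show other rates below.
- Encounters treated as independent.

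**Formula:** half-width = 1.96 × √(p(1 − p)/n).

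**Step 1. Try to reproduce ±8–10 at p = 0.80**

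- n = 40: 1.96 × √(0.16/40) = 1.96 × 0.0632 = 12.4 points.
- n = 80: 1.96 × √(0.16/80) = 1.96 × 0.0447 = 8.8 points.

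The stated range is not reproduced. Other methods at p = 0.80 do not recover it either:

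| Method | n = 40 | n = 80 |
|---|---|---|
| Wilson, 95% | 12.1 | 8.7 |
| Clopper-Pearson, 95% (average half-width) | 13.3 | 9.3 |
| Continuity-corrected, 95% | 13.7 | 9.4 |
| Simple formula at 90% confidence | 10.4 | 7.4 |

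The 90% row comes closest, but the plan specifies 95%.

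**Step 2. Encounters needed at p = 0.80**

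n = 1.96² × 0.16 / h².

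- h = 0.10: 61.5, so 62 per home.
- h = 0.08: 96.04, so 97 per home, above the planned maximum of 80.

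**Step 3. Other rates (assumed)**

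| Compliance | n = 40 | n = 80 |
|---|---|---|
| 50% | 15.5 | 11.0 |
| 70% | 14.2 | 10.0 |
| 80% | 12.4 | 8.8 |
| 85% | 11.1 | 7.8 |
| 90% | 9.3 | 6.6 |

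Forty encounters reach ±10 from about 88.2% compliance. Eighty encounters stay within ±10 from about 70.4% and reach ±8 from about 84.2%.

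**Step 4. Could one rate give 10 at n = 40 and 8 at n = 80?**

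Doubling n divides the half-width by √2 = 1.41, whereas 10/8 = 1.25. At 88.2% the pair is 10.0 and 7.1; at 84.2% it is 11.3 and 8.0. No single rate gives both.

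**Step 5. Both homes combined (n = 80 to 160) at 80%**

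1.96 × √(0.16/80) = 8.8 and 1.96 × √(0.16/160) = 6.2 points.

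**Step 6. What the minimum means in practice**

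An observed 32/40 (80%) in one home has a Wilson 95% interval of 65.2% to 89.5%. Both homes at the minimum, 64/80, give 70.0% to 87.3%.

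**The case against.** The strongest reply is that p = 0.80 is the reviewer's choice. The target is more than 80%, so 80% is the least favourable value within it. At 90% the half-widths are 9.3 and 6.6, at least as good as stated. This stands as a limit on the finding: compliance of about 88% or more removes the shortfall. But the plan states no such rate, and the precision has to hold at the threshold it wants to judge.

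A second reply is that the words about each nursing home attach to the count and not to the precision, and that the target is framed across both homes. Combined, the half-width is 8.8 to 6.2, so nothing is overpromised. The ambiguity is real and the text should settle it. Yet 8.8 to 6.2 is not 8–10 either. The parallel sentence for Objective 2 supports the per-home reading: 100 residents per home and period with ±4–6 points fits n = 100 at rates of 5% (4.3) to 10% (5.9).

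A third reply is that 8–10 may span a range of rates at one intermediate n. With n = 60 the half-width is 10.1 at 80%, 9.0 at 85% and 8.2 at 88%. That comes close, but 60 appears nowhere in the documents, and the sentence offers the precision for the whole range of 40 to 80.

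Finally, the practical effect is small. That is correct, and it limits the weight of the point without making the stated figure right.

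**Conclusion.** The concern holds. At 80% compliance, with 95% confidence and independent encounters, 40 to 80 encounters per home give ±12.4 to ±8.8 points against a stated ±8–10. The error lies at the low end: about 2 points beyond ±10 at n = 40, disappearing at about 62 encounters. At 62–80 encounters the half-width is inside ±10, though ±8 is not reached within the planned range at this rate.

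The conclusion rests on taking the target rate as the planning rate and on the per-home reading. Independence favours the plan: positive correlation between repeat observations of the same residents or staff would widen the interval, by an amount the documents do not allow to be calculated.

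This should be corrected, but its consequence is limited. No test or decision rule depends on the figure, and the reported intervals will reflect the data actually collected.

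**What to change.** Replace the precision sentence in Section 10.1 with one that names its assumptions, for example:

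*With 40 to 80 encounters in each home, an assumed compliance of 80% and encounters treated as independent, the 95% confidence interval will have a half-width of about 12 to 9 percentage points per home.*

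If precision across both homes is meant, say so and give about 9 to 6 points (80 to 160 encounters). Add a note that repeat observations of the same residents or staff would widen the interval if their outcomes are positively correlated.

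Optionally, compute the compliance interval with variance clustered on resident. That needs a resident code on the observation form; the Appendix lists only gown use and glove use for these observations.

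The cost is one sentence of planning text and a slightly less favourable figure. No extra observations are needed, and the planned analysis is unchanged unless the optional clustering is adopted.

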Nursing homes are healthcare settings that house a high prevalence of people with both MRSA and MSSA colonization, creating a high risk for resident-to-resident transmission of *Staphylococcus aureus* (SA). There is a mingling of long term and short term stay residents in community-based nursing homes which mix a population recovering from acute illness with a chronically ill population which has high prevalence of SA colonization. For example, we found that short stay residents are at four-fold higher risk for MRSA acquisition than long stay residents. Once SA acquisition occurs, people are at higher risk for infection as colonization typically precedes infection. Up to 30% of MRSA colonized patients develop an infection contributing to community onset invasive SA infections. Nursing home stay was identified as a common risk factor for invasive MRSA infection after recent hospital discharge.

Nursing home staff are the most frequent vector for SA transmission as their clothing and hands become contaminated with SA during the care of SA colonized residents. In contrast to hospitals, where the standard of care for patients with MRSA is Contact Precautions (gowns and gloves for all patient contact), community-based nursing homes typically use Standard Precautions (gowns and gloves for anticipated contact with blood, body fluids, skin breakdown or mucous membranes) for residents with MRSA. Prior research demonstrating high rates of MRSA acquisition in nursing homes suggests that Standard Precautions do not adequately reduce the transmission of SA.

Contact Precautions have not been widely adopted by nursing homes for several reasons. Nursing homes are resource-limited settings without the level of professional staff and laboratory infrastructure of hospitals. In addition, nursing home staff have deeply rooted beliefs that Contact Precautions stigmatize residents. There is a clear need for a solution - tailored to the nursing home setting - to reduce the risk of SA (and other antibiotic resistant bacteria) acquisition and infection. Our goal in this project is to demonstrate the feasibility of a novel intervention, targeted gown and glove use, to decrease SA acquisition and SA infection as a precursor for a future multisite stepped wedge cluster trial.

1.2 *Population*

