To adequately evaluate the study outcomes, it is critical that all or nearly all residents are included in the study. Obtaining authorization from 100% of residents is not practical in a nursing home due to many residents' lack of decision making capacity. Requiring authorization would bias the estimate of acquisition of SA since more ill residents will be less likely to provide authorization but may be more likely to acquire SA.

C. *Research could not practicably be conducted without access to and use of PHI*

To adequately evaluate the study outcomes, it is critical that we include basic clinical information as described in **11 Data Collection, Handling and Storage**. This includes important data such as

Preventing the Spread of Infection in Nursing Homes
whether residents are short stay or long stay which could affect the SA acquisition, an outcome variable and other data which will allow us to describe our population in aggregate.

7 Informed Consent for Health Care Workers (HCWs)

HCWs will participate in a number of ways. 1) Up to 10 HCWs will be shadowed in order to determine how to best implement the intervention, targeted gown and glove use. 2) Up to 6 staff will serve as liaisons to the project team. 3) HCWs will be observed during routine care in order to estimate gown and glove use. 4) All staff will wear disposable gowns and non-latex gloves while providing specific care for specific residents during the intervention period.

We request a waiver of documentation of informed consent (verbal/oral consent) for healthcare workers who are involved as research team liaisons or in shadowing to help develop this infection control intervention. This is a minimal risk study in which staff are being asked to participate as stakeholders in the development of an infection control intervention. The information collected is anonymous. If we were to use a consent document, the signed document would be the only link between the healthcare worker and the information.

We will not obtain informed consent for our observations of gown and glove use or the routine use of gown and gloves for providing specific care for specific residents during the intervention period because this will be standard practice in the nursing home as agreed upon by the participating NH (see below, **7.1 Recruitment Process**).

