APPENDIX: Study Variables**Table: Study Variables**

Ascertained				
Variables	When	How	Purpose	Format
RESIDENT CHARACTERISTICS (measured once on each subject)				
Identifying information- Name as appears in existing medical record at LTCF	Enrollment	Existing medical record at LTCF (MR)	Looking up information in MR	Nominal
Medical record number	Enrollment	MR	Looking up information in MR	Ordinal
SSN	Enrollment	MR	Looking up information in MR	Nominal
Demographics				
Level of Care	Enrollment	MR	Study variable	Nominal: Rehabilitation, Skilled Nursing, Maintenance
Short Stay	Enrollment	MR	Study variable	Yes/no
Unit in Facility	Enrollment	MR	Descriptive	Nominal: from list of units in participating LTCFs
Age	Enrollment	MR	Descriptive	Interval
Sex	Enrollment	MR	Descriptive	Nominal
Race	Enrollment	MR	Descriptive	per OMB Directive 15 definitions
Ethnicity	Enrollment	MR	Descriptive	per OMB Directive 15 definitions
Length of Stay in LTCF prior to Enrollment	Enrollment	MR	Descriptive	Interval
Charlson Co-morbidity Index	Enrollment	MR	Descriptive	Ordinal: 0-37
Dependence with ADLs	Enrollment	MR	Descriptive	Ordinal: 1 - minimal assistance, 2 - moderate assistance, 3 - requires assistance with most ADLs
Katz ADL (5)	Enrollment	MR/MDS	Descriptive	
History of colonization or infection with Multidrug Resistant Organism	Enrollment	MR	Descriptive	Yes/no
Types of Medical Devices:				
Urinary catheter	Enrollment	MR	Study variable	Yes/no
Venous catheter for parenteral medications	Enrollment	MR	Study variable	Yes/no
Gastro or jejunostomy tube for enteral nutrition	Enrollment	MR	Study variable	Yes/no
Other	Enrollment	MR	Study variable	Nominal
Type of skin breakdown:			Study variable	

Preventing the Spread of Infection in Nursing Homes

Ascertained				
Variables	When	How	Purpose	Format
Pressure ulcer	Enrollment	MR	Study variable	Yes/no
Unhealed surgical incision	Enrollment	MR	Study variable	Yes/no
Percutaneous medical device	Enrollment	MR	Study variable	Yes/no
Tracheostomy	Enrollment	MR	Study variable	Yes/no
GI Ostomy	Enrollment	MR	Study variable	Yes/no
Other	Enrollment	MR	Study variable	Nominal
HEALTHCARE SETTING FACTORS (measured once per facility)				
Facility (Study Site)	Facility Start-up		Descriptive	Nominal: from list of participating NHs
Number of Licensed beds	Facility Start-up	Administrator	Descriptive	Interval
Number of current beds	Facility Start-up	Administrator	Descriptive	Interval
Units	Facility Start-up	Administrator	Descriptive	Nominal: from list of units

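### The before-after acquisition ratio in each home takes no account of short-stay status, which the protocol links to acquisition and records for every resident

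*Combined protocol and SAP*

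**What the plan says.** Section 10.1 models the risk of acquisition between swabs as 1 − exp(−λt), where t "is the number of days between swabs and λ is interpretable as the daily rate of acquisition". It continues: "We will estimate λ in the baseline and intervention periods using maximum likelihood estimation and compare the two rates". A likelihood confidence interval for the ratio follows, and "This will be done for each nursing home separately". Time between swabs is the only resident-level term. No covariate, stratum or sensitivity analysis for acquisition appears there or elsewhere.

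The protocol treats stay type as relevant to this outcome in three places:

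- Section 1.1: "we found that short stay residents are at four-fold higher risk for MRSA acquisition than long stay residents".
- Section 6.3, in justifying access to records: "whether residents are short stay or long stay which could affect the SA acquisition, an outcome variable".
- The Appendix lists short stay (yes/no, at enrollment) as a study variable, while age, sex and race are listed as descriptive.

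The Appendix also lists "Proportion of Beds- Short stay" among the facility factors, measured once at start-up. Section 3.1 makes the change in acquisition rate the primary outcome and adds: "The observed SA acquisition rate reduction from this pilot study will be used to estimate the effect size".

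**The concern.** Making each home its own control (section 3.2) removes fixed differences between homes. It does not deal with a change in who is living in a home between two separate two-month periods. Residents enter on admission and leave on discharge, so the two groups are not the same people.

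The model allows for length of exposure through t, but it assumes one daily rate for everyone in a period. If short-stay residents have a higher daily rate and their share changes systematically, the fitted λ changes even when the intervention does nothing. A falling share looks like benefit and a rising share looks like harm. The start-up bed proportion cannot show such a change. The resident-level variable can, but the analysis does not use it.

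At stake are the primary comparison in each home, the planning effect size, and the impression of between-home variation that section 10.1 also wants. The last would be distorted if the mix moved differently in the two homes.

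**Working it through.** **Inputs from the documents.** 100 residents per home per period and a stated precision of ±4-6 percentage points (section 10.1); swab interval up to 60 days (section 8.1); four-fold risk for MRSA (section 1.1).

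**Assumptions, because the documents give no values.** Short-stay share 50% at baseline, falling to 40% or 36%; short-stay interval 15, 20 or 30 days; long-stay interval 60 days; no intervention effect. The four-fold figure is for MRSA and is stated as a risk. It is used here as a daily rate ratio R for all *S. aureus*, so R = 2 and R = 1.5 are shown as well.

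**1. The plan's own precision figure.** Setting 1.96·√(p(1−p)/100) equal to 0.04 gives p = 4.35%, and equal to 0.06 gives p = 10.5%. The stated precision therefore fits about 4 to 10 acquisitions per home per period. No expected proportion is given, so the figure is consistent but cannot be reproduced independently.

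**2. From share of residents to share of person-time.** With short-stay share f and a 20-day short-stay interval, the short-stay share of person-time is s = 20f / (20f + 60(1−f)).

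- f = 50%: 10/40 = 25%
- f = 40%: 8/44 = 18.2%
- f = 36%: 7.2/45.6 = 15.8%

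**3. Expected crude ratio with no intervention effect.** To a close approximation it is (1 + (R−1)s₁) / (1 + (R−1)s₀), where s₀ and s₁ are the baseline and intervention shares. At R = 4, a fall from 50% to 40% gives (1 + 3×0.182)/(1 + 3×0.25) = 1.546/1.75 = 0.88. A fall to 36% gives 1.474/1.75 = 0.84. Solving the expected score equation of the constant-λ likelihood over 15-, 20- and 30-day short stays gives:

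| Rate ratio R | 50% → 40% | 50% → 36% |
|---|---|---|
| 4 | 0.875-0.893 | 0.830-0.856 |
| 2 | 0.937-0.952 | 0.915-0.936 |
| 1.5 | 0.964-0.974 | 0.951-0.965 |

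On the log scale the bias runs from about 0.03 (−ln 0.974) to 0.19 (−ln 0.830). It is symmetric in kind: with R = 4 and short stays of 20-60 days, a rise from 40% to 50% gives 1.13-1.14. An unchanged mix gives 1.00.

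**4. Effect of adding short stay.** Simulation of one home, 100 residents per period, 20/60-day intervals, no effect, acquisition at the two levels from step 1, 6,000 data sets per setting, share fixed at 50% then 36%:

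- Geometric mean crude ratio: 0.83-0.84 at R = 4 and 0.90-0.92 at R = 2.
- Geometric mean adjusted ratio: 0.98-1.00.
- SD of the log ratio: 0.46-0.74 crude, 0.47-0.75 adjusted, an increase of 0.9-1.6%.

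A separate simulation (R = 4, 30/60 days, 50% to 30%) gave a median ratio of 0.76 crude and 1.00 adjusted, with median standard errors of 0.587 and 0.597 (0.597/0.587 = 1.017).

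**5. Chance variation in mix.** With the share varying at random around 50% in both periods, the mean crude ratio was 0.99-1.01. Chance swings add sampling error, not bias.

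**6. Sparse data.** At 4.35% acquisition, 39-46% of simulated homes had at least one stay-by-period cell with no events; at 10.5% it was 2-5%. About 5-7% of homes at 4.35% had no events in a whole period or stay type and were left out, so the standard-error cost in step 4 applies to the remaining homes.

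**The case against.** The strongest reply is that the bias depends on something the documents do not suggest will happen. The periods are one month apart in the same home and use the same swabbing procedure, and the shift assumed above is not from the protocol. The largest figures also rest on an MRSA ratio, while the outcome is all *S. aureus*.

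Even if the shift occurs, random error dominates within one home. Combining bias and variance for the log ratio at R = 4 and the worst shift:

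- Crude: √(0.46² + 0.186²) = 0.496, or √(0.74² + 0.186²) = 0.763.
- Adjusted: 0.464-0.467, or 0.747-0.752.

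That is a gain of about 1.5-7%. At R = 2 there is no clear gain, and at R = 1.5 the adjusted estimate is slightly worse.

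It can also be said that other high-risk features (wounds, devices, dependence) are left out, that short stay is itself a targeting criterion so the effect may differ by stay type, and that a fallback for empty cells makes the estimator depend on the data.

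Most of this stands as a limit on size. It does not remove the point. The loss from adjusting is at worst 1-2%, and a check with a true intervention effect showed almost no cost. The confidence interval conveys sampling error but not a shift in mix, and the bias would not shrink if homes were combined. Short stay is the one factor for which the protocol itself gives an acquisition ratio. The sparse cells are a good reason not to interpret stay-specific effects, and a reason to write the fallback down beforehand.

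**Conclusion.** The concern holds. The plan fits one unadjusted rate per period in each home and leaves out a factor that its own text ties to the outcome and already collects. Nothing else in the documents handles a change in resident mix.

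The omission is certain; the size of its effect is conditional. It requires a systematic change in short-stay share and a higher short-stay daily rate for *S. aureus*. Under the assumptions shown, the log-scale bias of 0.03-0.19 compares with a sampling SD of about 0.46-0.75, so it would not dominate the result in one home. It matters because the ratio is the primary comparison and feeds the next trial's effect size, and because prespecifying the adjustment is more credible than choosing it after seeing a small, noisy result. It is worth changing, with medium confidence about its practical importance.

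**What to change.** Keep the likelihood and the analysis by nursing home, and amend section 10.1 as follows:

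- Within each home, let log λ depend on period and short stay (binary model with complementary log-log link and offset log t). Make the adjusted period ratio, with its likelihood interval, the main estimate.
- Report the short-stay share of residents and of person-time by period and home, with the crude ratio as a sensitivity result.
- Present stay-type-specific rates as descriptive only, since events will be few.
- State in advance that if a home has no events in one stay type, its crude ratio is reported with the shares.
- If a combined estimate is wanted, add home and a home-by-period term, or report it in addition to the home-specific ratios.

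The cost is one extra parameter per home, no new data collection, and about 1-2% more standard error in simulation. The adjustment deals with stay type only; other changes between the periods remain a limit of the before-after design.
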